13.2. The number of participants

Maximum 250, inclusion time 4 months.

13.3. The level of statistical significance

For all analyses, the level of significance will be 5% two-sided significant level.

13.4. Criteria for the termination of the clinical investigation

Clinical investigation will be terminated after the postoperative visit on the day after the surgery.

13.5. suspension or premature termination of the trial

In case of suspension or premature termination of the trial a notification will be sent in writing to the CA and EC explaining the reason behind this decision.

13.6. Procedure for accounting for missing, unused and spurious data

Missing data will be reported with reasons given where available, and the missing data pattern will be examined. We will explore the mechanism of missing data (MCAR, MAR) by means of the Jamshidian & Jalal's (2010)'s test for MCAR or logistic regression models for MAR which will explore if missingness (i.e. whether the primary outcome is missing or not) is related to measured baseline variables. As indicated by Molenberghs et al. (2008), one can never totally exclude a MNAR process, but every MNAR model has a MAR counterpart with equal fit. Therefore, in case of MCAR, MAR or MNAR missing processes, Maximum Likelihood (ML) and Multiple Imputation (MI) can be used, using the mice R package for the last one (Raghunathan et al., 2001; van Buuren & Oudshoorn, 2000), with a predefined seed. Indeed, ML and MI uses all available data in the study, produces unbiased estimates of the treatment effect and correct p-values. MI is also a method of choice because it

allows not only to impute missing values on the outcome but also on the covariate (Dziura et al., 2013) and is valid for MCAR, MAR and MNAR (Molenberghs et al., 2008).

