- The infusion line can connect to the infusion canula without the need to remove its sealing cap. This reduces the amount of surgical movements and allows better surgical flexibility when the infusion needs to be switched to another instrument cannula during surgery.
- The infusion line locks onto the infusion canula, reducing the incidence of a commonly occurring issue that the infusion line disconnects from the cannula during the surgery.

After brought under anesthesia, the patients is draped while the vitrectomy device is being prepared. This involves connecting of all the surgical supplies (see above) and priming of the device. This whole procedure takes 10-20 minutes, depending on the complexity of

the case. The packaging of the surgical supplies was reworked (reduction in the amount of packaging materials) and the infusion giving set has been simplified significantly for the EVA Nexus platform. This should shorten the total surgical time.

Surgical issues and/or (S)AE's that are related to the surgical device will always be observed either during the surgery or during the postoperative visit on day one. Late-onset complications such as proliferative vitreoretinopathy, retinal detachment etc. are considered non-related to the surgical device. Hence, in this study, data acquisition is terminated after the postoperative visit on day one, although the patient will have further postoperative follow-up according the standard of care.

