6. OBJECTIVES

The primary objective and primary parameters are shown in the table below:

The main purpose of this study is to evaluate the intra-operative safety of a new surgical device.
	
Therefore, having no idea of the percentage of patients having complications, we make the hypothesis that minimum 5% of the patients will have complications. In order to make sure that we have at least 10 patients with complications, we plan recruit 250 patients in total in order to get at least 10 complications with EVA Nexus.
 
For this purpose, typical surgical parameters will be recorded during vitrectomy surgery:
 
 • Surgical indication • If combined phaco-surgery is performed: amount of phaco power used • Staining dyes (if used) • Amount of laser coagulates (if used) • Type of tamponade left in the eye: BSS+ liquid, air bubble, air, gas (type + concentration) or silicone oil (type) 
Specific adverse events that may occur during (phaco)vitrectomy will be recorded to assess the surgical safety ¹⁵⁻¹⁸: see list in Appendix A. This AE reporting is already present in the surgical report (KWS-Formasa) used for daily vitrectomy surgery using the DORC EVA device. The occurrence of these AE's during surgeries using the EVA Nexus will be compared to historical data retrieved from surgeries using the DORC EVA platform.
 
Device issues that caused some hindering during the surgery but that do not lead to an (S)AE, such as error messages/warnings that did occur, malfunctioning of supplies that required replacement etc. will be recorded.
 
See Appendix B for a full list, which is already part of our present surgical report (KWS-Formasa). The occurrence of these issues during surgeries using the EVA Nexus will be compared to historical data retrieved from surgeries using the DORC EVA platform.

---	---

The secondary objective and secondary parameters are shown in the table below:

Secondary objective	Secondary parameters
To evaluate the possible reduction of total surgical time.	The time that was required to prepare the EVA Nexus will be recorded (connecting of supplies + priming). During the study period, this time will also be recorded during surgeries performed with the DORC EVA device for comparison.

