8. CLINICAL INVESTIGATION POPULATION

8.1. Number of participants – sample size analysis

With a complication rate ranging from 5% up to 30% in previous studies, we have no a priori about the complication rate of the EVA Nexus system. We therefore consider a rather conservative hypothesis and expect to have around 5% of complications with the EVA Nexus system. We plan recruit 250 patients in total in order to get at least 10 complications with EVA Nexus. The estimated enrolment time is 6 months.

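### Section 13.6 claims that maximum likelihood and multiple imputation are unbiased and valid under MNAR, which is wrong as written, and plans no sensitivity analysis

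*Combined protocol and SAP*

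**What the plan says.** Section 13.6 will report missing data with reasons, examine the pattern, and explore the mechanism with an MCAR test and with logistic models of missingness on baseline variables. It then accepts that "one can never totally exclude a MNAR process" and adds that "every MNAR model has a MAR counterpart with equal fit". From this it concludes that "in case of MCAR, MAR or MNAR missing processes, Maximum Likelihood (ML) and Multiple Imputation (MI) can be used". It says that this approach "produces unbiased estimates of the treatment effect and correct p-values", with no MAR condition attached. It closes by saying of multiple imputation that it can fill in both outcome and covariates "and is valid for MCAR, MAR and MNAR". The software (mice) and a predefined seed are named.

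The primary analysis (sections 13.1 and 14.5) is a one-sample proportion test of the complication rate against 30%, 15% and 5%, at the two-sided 5% level of section 13.3. Neither section contains an MNAR model, bounds or a tipping-point analysis. Section 13.8 includes all patients and gives no rule for a missing outcome.

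Sections 9.1 and 9.2 place consent on the evening after surgery and bar use of the record without a signature. Section 9.1 has every operated patient asked and the number of refusals listed. The planned analysis gives that number no place.

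**The concern.** The inference in section 13.6 runs the wrong way. If an MNAR model and a MAR model fit the observed data equally well, the data cannot tell them apart, yet the two may imply different complication rates. That is a reason for a sensitivity analysis, not a proof that a MAR-based method is valid under MNAR. The planned diagnostics cannot settle the matter either, as the section itself accepts.

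The study's main purpose is to evaluate intra-operative safety. If complicated cases are missing more often, a MAR-based rate is too low. The report could then call that rate unbiased, with correct p-values, under a mechanism that the plan says it cannot exclude.

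Refusals are a separate matter, because refusers are outside the dataset and section 13.6 cannot impute them. Asking every patient deals with selection by the surgeon. It does not deal with refusal related to how the operation went, which is possible when consent follows surgery. The documents give no refusal rate, so the size and direction of any bias are unknown.

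**Working it through.** **Inputs from the documents.** 250 patients, and "expect to have around 5% of complications with the EVA Nexus system" (section 8.1); comparison rates of 5%, 15% and 30% (sections 13.1 and 14.5); two-sided 5% level (section 13.3). Section 13.6 states no figure of its own to reproduce. The 250 of section 8.1 is not disputed: at 5% it gives 250 × 0.05 = 12.5 expected complications, and P(at least 10) = 0.805.

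**Assumptions.** The documents give no missing-data or refusal rate, so every count below is illustrative. I take 12 complications, and all tests are exact two-sided binomial.

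**Step 1: base case.** 12/250 = 4.8%: p=1.0 against 5%, p<0.001 against 15% and 30%.

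**Step 2: equal fit does not identify the rate.** Let 5 of 250 statuses be missing, with 12 complications among the 245 known (12/245 = 4.9%). The known data are identical whether none or all of the 5 had a complication: 12/250 = 4.8% or (12+5)/250 = 6.8%. With 2 missing the range is 4.8% to 14/250 = 5.6%.

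**Step 3: bias of a MAR-based estimate under MNAR.** Let p be the true rate, and m1 and m0 the probabilities of a missing status with and without a complication. Without predictive covariates the estimate tends to p(1−m1) / [p(1−m1) + (1−p)(1−m0)]. For p = 0.05, m0 = 0.10 and m1 = 0.20: 0.040 / (0.040 + 0.855) = 4.5%. Other cases:

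| m0 | m1 = 2×m0 | m1 = 4×m0 |
|---|---|---|
| 2% | 4.9% | 4.7% |
| 5% | 4.7% | 4.2% |
| 10% | 4.5% | 3.4% |

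Proper logistic multiple imputation was also simulated (n=250, 20 imputations, one predictive covariate, 1,500 runs, true rate 5%):

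| m0 / m1 | Mean estimate | Coverage of nominal 95% interval |
|---|---|---|
| 10% / 10% (MCAR) | 5.0% | 94% |
| 10% / 20% | 4.5% | 89% |
| 5% / 20% | 4.25% | 86% |
| 10% / 40% | 3.5% | 70% |

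Neither the unbiasedness nor the correct inference survives under MNAR.

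**Step 4: how many missing statuses would matter.** With m missing patients, all with complications, the rate is (12+m)/250.

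| m | Rate | Result |
|---|---|---|
| 2 | 14/250 = 5.6% | p=0.66 against 5%; nothing changes |
| 5 | 17/250 = 6.8% | p=0.19 against 5%, 0.0001 against 15%; nothing changes |
| 8 | 20/250 = 8.0% | p=0.040 against 5%: first change (19/250, p=0.079) |
| 15 | 27/250 = 10.8% | p=0.063: 15% result lost (26/250, p=0.041) |
| 38 | 50/250 = 20.0% | p=0.033: 15% result reversed |
| 49 | 61/250 = 24.4% | p=0.053: 30% result lost |

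**Step 5: refusals (optional part).** Bounds are 12/(250+R) to (12+R)/(250+R) for R refusers on top of 250 enrolled.

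- R=28 (28/278 = 10% of those asked): 4.3% to 14.4%. The 5% result changes from 10 of 28 with complications (22/278, p=0.037). The 15% result is lost from 18 of 28 (30/278, p=0.053) and is not reversed.
- R=50 (50/300 = 17%): 4.0% to 20.7%. The 5% result changes from 11 of 50 (23/300, p=0.045). The 15% result is lost from 21 of 50 (33/300, p=0.052) and reversed from 46 of 50 (58/300, p=0.043).
- In both cases the 30% result stands, and at the low bound nothing changes. With fewer than 9 refusers no comparison can change (9 refusers: 21/259, p=0.031 against 5%).

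These tipping points need complication rates among refusers between 11/50 = 22% and 46/50 = 92%.

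**The case against.** The strongest reply is that missing primary outcomes should be rare. On the complications list, section 6 notes that "This AE reporting is already present in the surgical report", and section 5.3 says that "data acquisition is terminated after the postoperative visit on day one". The adverse-event form in Appendix C makes its opening question mandatory, and the vitrectomy list in Appendix A has an explicit entry for no complication. The lens list shows no such entry, which may only reflect how the form was extracted. At 2% base missingness the bias in step 3 is at most 0.3 percentage points. The thresholds of 38 and 49 missing would mean 15% to 20% of outcomes lost; they also hold 12 events fixed while the known denominator shrinks, to 12/201 = 6.0% in the last case. The wording of section 13.6 is permissive, and section 13.7 leaves the final statistical plan open until before data lock. The refusal scenarios are assumed, and their bounds mainly reflect the assumed number of refusers.

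Most of this stands as a limit on size: few missing statuses are likely, and the larger thresholds are remote. It does not rescue the statement itself. The claim of validity under MNAR is the stated justification for the method, and nothing else in the statistics sections corrects it. An open final plan is an opportunity to correct the text, not a correction. The point on refusals is met by treating that part as optional.

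**Conclusion.** The concern holds. Section 13.6 attributes to maximum likelihood and multiple imputation a property they do not have under MNAR, a mechanism that the section itself says cannot be excluded, and no sensitivity analysis covers the gap. The change should be made, but it is a correction of a stated property and of planning, not of the sample size. The likely numerical effect is small: under the assumed 12 complications in 250, neither 2 nor 5 missing statuses alters any of the three comparisons, and 8 missing patients, all with complications, are needed before one does. This rests on assumed counts and exact binomial tests. The refusal count is a separate and optional matter whose size and direction cannot be judged from the documents.

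**What to change.** - In section 13.6, restrict the statements on validity, unbiasedness and correct p-values to MCAR or MAR with a correctly specified imputation model, and drop the inference from equal fit. Replace the reference to a treatment effect with the complication rate, since the primary analysis has one sample.
- Pre-specify one sensitivity analysis of the primary rate: count missing statuses among consenting patients as all complications and as none, and give the number of missing patients with complications at which each comparison (5%, 15%, 30%) changes.
- Optional: report the refusal count beside the primary rate, with the same bounds and with tipping points in both directions, and state that the size and direction of any bias are unknown. Section 9.1 needs no change.

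All of this can go into the final statistical plan due before data lock (section 13.7). The cost is a few words and one table. No data from refusers are needed beyond the count already kept, and sample size, visits and consent are unaffected. If few statuses are missing, the table will be short and will show that the result is robust. The drawback is that all-or-none bounds for refusals can be much wider than the estimate in consenting patients, so the tipping points should be shown with them.

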13.7. Procedures for reporting any deviations from the original statistical plan

The final statistical plan will be agreed prior to final data lock and prior to any analyses taking place. Any deviation thereafter will be reported in the final trial report.

13.8. Inclusion in analysis

All patients will be included in the trial.

14. Clinical investigation management group and parties involved

14.1 The clinical investigation management group consists of the following participants:

Principal Investigator

Name: [name]
Title: Vitreoretinal surgeon

Address:
UZLeuven
[name]
[name]
[contact]
Email: [contact]

Statistician

Name: [name], Ars Statistica
Title: Bio-Statistician

Address:
[name]
[name]
Email: [contact]

Clinical investigation Management

Name: [name]
Title: CRA

Address:
Ophthalmology
UZLeuven E 107
[name]
[name]
[contact]
Email:
[contact]

Clinical investigation Coordination Centre

For general queries, supply of clinical investigation documentation, and collection of data, please contact the Clinical Investigation Coordinator:

Name: [name]

Address: [name]

[contact]

Email:

[contact]

Clinical Queries

Clinical queries should be directed to [contact] who will direct the query to the appropriate person

Investigation site

Name: UZ Leuven E107
Address: [name]
[contact]
Email: [contact]

Sponsor

Name: UZ Leuven
Address: [name]
Telephone:
Email: [contact]

Funder

Name: DORC B.V.
Address: [name]
[contact] and [contact]
Email: [contact]

14.2 Clinical investigation steering committee

N/A

14.3 Data monitoring committee

N/A

14.4 Monitoring plan

The study protocol was reviewed by the CTC prior to study approval. In case the CTC decides to appoint a monitor for this trial, the monitor will be able to visit the Investigator site prior to the start of the clinical investigation and during the course of the clinical investigation if required, in accordance with the monitoring plan. In such case, monitoring can be performed according to ISO 14155:2011.

Data will be evaluated for compliance with the clinical investigation plan and accuracy in relation to source documents. Following written standard operating procedures, the monitors will verify that the clinical investigation is conducted and data are generated, documented and reported in compliance with the clinical investigation plan, GCP and the applicable regulatory requirements.

14.5 Statistical Analysis plan

13.13.1. Descriptive statistics

Summary statistics (Nb observations, minimum, Q_{25} , median, Q_{75} , maximum, standard deviation) of the whole studied group will be provided.

13.13.2. Primary outcome

For the primary endpoint (complication rate of the EVA Nexus), a one-sample proportion test will be performed to test whether the obtained rate is different from rates found in the literature (30%, 15% and 5%).

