7. CLINICAL INVESTIGATION DESIGN

7.1 Trial Design

Investigator-initiated, academic, mono-center, prospective, field observation study using a novel CE-labeled surgical platform.

The study will be terminated after a time period of three months. A maximum of 250 patients will be enrolled. The study will consist of 3 patient visits. Study follow-up is 1 day after the date of the vitrectomy surgery.

During surgery, intra-operative complications and issues will be recorded for safety assessment: see list in previous paragraph.

Typical postoperative follow-up after vitrectomy includes the clinical tests to assess that normal postoperative outcome is present, without the presence of adverse events.

Hence, the same clinical data will be collected in the study patients as in patients undergoing the standard-of-care.

This field observation study is conducted to obtain information about the complication rate of the EVA Nexus system which will be compared with the incidence of these complications occurring in surgeries performed using our present DORC EVA platform. ¹⁵⁻¹⁸

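### The primary analysis tests one complication rate against 30%, 15% and 5% with no reference value and no confidence interval; at 250 patients at least two tests are significant whatever the result

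*Combined protocol and SAP*

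**What the plan says.** Section 13.1, and sections 13.13.2 and 13.13.3 under 14.5, give the same primary analysis, a one-sample proportion test "to test whether the obtained rate is different from rates found in the literature (30%, 15% and 5" per cent). Section 13.3 adds: "For all analyses, the level of significance will be 5% two-sided significant level". None of these sections says which of the three values is the reference, which direction would be reassuring, or how the three results are to be read together.

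The purpose is estimation. Section 7.1 states: "This field observation study is conducted to obtain information about the complication rate of the EVA Nexus system". Yet the descriptive statistics in 13.13.1 are counts, quartiles, extremes and a standard deviation, and no section plans a confidence interval for the complication rate.

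On size, section 8.1 says "With a complication rate ranging from 5% up to 30% in previous studies, we have no a priori about the complication rate", then that the investigators "expect to have around 5% of complications with the EVA Nexus system", and then "We plan recruit 250 patients in total in order to get at least 10 complications with EVA Nexus". No power, margin or performance goal is given. Section 13.2 treats 250 as a ceiling: "Maximum 250, inclusion time 4 months".

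Sections 6 and 7.1 also promise a comparison with surgeries done on the existing DORC EVA platform. The statistics sections contain no method for it.

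**The concern.** The three null values exclude one another, so at most one can be true. If the sample is large enough to separate them, some of the tests must reject whatever the device does. A report that the complication rate differed significantly from published rates would then be certain in advance for a device with few complications and for one with many. The number of significant tests would carry no safety message.

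A second problem is what a non-significant result means. A two-sided test that fails to reject 5% does not show a rate of 5% or lower. Without an interval, the reader cannot see how high the true rate might be. This is the sole primary analysis of a study whose stated purpose is to learn the complication rate and evaluate intra-operative safety.

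**Working it through.** **Inputs.** n = 250 as a maximum (sections 7.1, 8.1, 13.2); null values p0 = 0.05, 0.15 and 0.30 (13.1, 13.13.2, 13.13.3); alpha = 0.05 two-sided (13.3); expected rate about 5% (8.1).

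**The plan's own figure.** The expected count at 5% is 250 × 0.05 = 12.5. With X ~ Binomial(250, 0.05), P(X ≥ 10) = 0.805. So 250 patients give about an 80% chance of at least 10 complications. The smallest n reaching 80% is 249. The 80% level is an assumption, because the plan states no probability. The figure of 250 is reproduced on that basis, but it sizes a count of events and not any of the three tests.

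**Which counts reject which value.** For each x from 0 to 250, the exact two-sided p-value is the sum of P(X = k | n = 250, p0) over all k no more probable than x. The counts with p ≥ 0.05 are:

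| Null value | Non-rejecting counts | Observed rate |
|---|---|---|
| 5% | 6–19 | 2.4%–7.6% |
| 15% | 27–49 | 10.8%–19.6% |
| 30% | 61–89 | 24.4%–35.6% |

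No count appears in two rows, so every possible result rejects at least two of the three values. All three are rejected at 0–5, 20–26, 50–60 and 90 or more complications.

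**Does the choice of test matter?** The plan does not name the version of the one-sample test. The ranges shift by a count or two but stay disjoint for the score test (6–19, 27–48, 61–89), the score test with continuity correction (6–19, 26–49, 61–89), the doubled-tail exact test (6–20, 27–49, 61–89) and the Wald test (8–21, 28–49, 62–89). They also stay disjoint for all five versions at alpha/3.

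**Does it survive under-recruitment?** With the exact test, at least two rejections are certain for every n from 126 to 250. At n = 125 the ranges for 5% and 15% are 2–11 and 11–26, so 11 complications reject only 30%. The largest n at which the guarantee can fail is 125 for the exact and score tests, 138 with continuity correction and 143 for the doubled-tail exact test.

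**Probability that all three tests reject (exact test, n = 250).** This is 1 minus the summed probabilities of the three non-rejection ranges.

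| True rate | All three reject |
|---|---|
| 5% | 4.0% |
| 8% | 46% |
| 9% | 55% |
| 10% | 51% |
| 15% | 4.1% |
| 20% | 47% |
| 30% | 4.5% |

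**What an interval would show (Clopper-Pearson, 95%).**

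| Result | Rate | Exact 95% interval |
|---|---|---|
| 12/250 | 4.8% | 2.5% to 8.2% |
| 19/250 | 7.6% | 4.6% to 11.6% |
| 25/250 | 10.0% | 6.6% to 14.4% |
| 75/250 | 30.0% | 24.4% to 36.1% |

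The first two rows give the same pattern of tests: 5% not rejected, 15% and 30% rejected. Their upper limits differ by 11.6 − 8.2 = 3.4 percentage points.

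**The case against.** The strongest reply is that the three tests are not meant as one verdict. Section 8.1 reports published rates from 5% to 30% and claims no prior expectation, so placing the new rate within that range is a coherent, if crude, aim. Disjoint non-rejection ranges are what allow it. At 12/250 the exact p-values are 1.0 against 5%, about 5 × 10⁻⁷ against 15% and about 2 × 10⁻²³ against 30%, which reads plainly as well below the two higher values and compatible with the lowest. At the planned 5% rate this is the usual outcome: all three reject only 4% of the time. This stands. A reader might infer that the primary analysis is empty, or can neither support nor count against safety; the documents do not support that. Only the bare finding of a difference is uninformative.

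A reader might also infer that the authors are free to pick a favourable comparison afterwards. All three tests are prespecified in identical words, and section 13.7 has the final statistical plan agreed before data lock, with later deviations reported. Omitting one would be visible. What remains open is emphasis, because no value is named as the reference.

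Nor is this mainly inflated type I error. Only one null can be true, and the exact error is 4.0%, 4.1% and 4.5% at 5%, 15% and 30%. A multiplicity correction would not help.

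Finally, this is an observational study of a CE-labelled device and claims no confirmatory test. That stands too, and it favours an interval over three hypothesis tests.

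**Conclusion.** The concern holds in a limited form. With 250 patients, at least two of the three primary tests are significant whatever the result, so a statement that the rate differs from literature rates is certain in advance. The pattern and direction of the tests locate the rate roughly. They do not give its precision, and not rejecting 5% leaves rates well above 5% open, as 19/250 shows.

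The chance that all three reject depends strongly on the true rate: about 4% at the planned 5%, and 46% to 55% at true rates of 8% to 10%. The higher figures belong to rates that the plan does not name and should not be read as the expected outcome.

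The guarantee assumes more than 125 patients with the exact test, or more than 143 with the most demanding of the versions checked for this. That is not assured. Section 7.1 stops the study at three months, while 8.1 estimates six months to enrol. At a constant rate, an assumption, that gives 250 × 3/6 = 125 patients, just below the limit. The missing reference value and missing interval do not depend on the number enrolled.

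**What to change.** In sections 13.1, 13.13.2 and 13.13.3, make the primary result the proportion of patients with a complication and its exact (Clopper-Pearson) 95% confidence interval. Show 5%, 15% and 30% as reference values read against that interval, without separate significance claims.

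A formal test is optional. If the sponsor wants one, the plan should name and justify one reference value and a direction before any analysis. The historical DORC EVA rate promised in sections 6 and 7.1 is a candidate. It would have to be retrieved and justified, and a two-sided test against it would still not show acceptable safety.

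The interval needs no further patients, visits or data. The cost is a small change to protocol and SAP text, with the amendment steps of section 15.1 where they apply, and fewer p-values to quote. Section 13.7 leaves room for it, since the final statistical plan is to be agreed before data lock.
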